If any personal health information or confidentiality is compromised, then we will notify all patient's caregivers enrolled in the study in order to alert them to the issue. At that point, the study will be stopped until further investigation and evaluation can be performed to ascertain if in fact a breach of personal health information or confidentiality has occurred. If in fact it has occurred, the Institutional Review Board will be notified and all aspects of the study will be postponed until the situation has been resolved. While we do not anticipate serious adverse events, in the unlikely event they do occur, they will be immediately reported to IRB.

c. If hazards occur that might make the risks of participation outweigh the benefits for all participants, describe (i) the criteria that will be used to stop or end the entire protocol and (ii) any special procedures, precautions, or follow-up that will be used to ensure the safety of currently enrolled participants. Not Applicable

21. Informed Consent

a. Do you plan to obtain informed consent for this protocol? Yes No
If Yes, complete the items below.
If No, complete and include the [Waiver of Informed Consent](#) or [Waiver of Authorization and Informed Consent](#), as applicable.

b. Do you plan to document informed consent (obtain signatures) for this protocol? Yes No
If Yes, complete the items below.
If No, complete the items below and include the [Waiver of Informed Consent Documentation](#).

c. How will consent be obtained? Study investigators/study coordinator/research assistant will obtain informed consent in the emergency department once potential patients are identified.

d. Who will conduct the consent interview? Study key personnel as listed in section 3.

e. Who are the persons who will provide consent, permission, and/or assent? If patient is less than 7 years of age, parent/legal guardian will provide consent. If patient is 7-13 years, patient will provide assent and parent/legal guardian will provide consent. If patient is 14 years but less than 18 years, patient and parent/legal guardian will sign the consent form.

f. What steps will be taken to minimize the possibility of coercion or undue influence? We will adhere strictly to our consent and assent forms and if a patient or caregiver expresses discomfort with participation (beyond having further questions), the study staff will be instructed to thank them for their time and document them as having refused participation.

g. What language will the prospective participant and the legally authorized representative understand? They will not be expected to understand anything more than an 8th grade reading level.

h. What language will be used to obtain consent? English will be used. Strictly for purposes of convenience for the Emergency Department and Children's of Alabama Interpreter Services any non-english speaking caregivers will be excluded from the study.

i. If any potential participants will be, or will have been, in a stressful, painful, or drugged condition before or during the consent process, describe the precautions proposed to overcome the effect of the condition on the consent process. If not, enter "None." In such situations, the treating physician will stabilize patients before informed consent process. Additionally, the person obtaining consent we will allow enough time for patients to understand the study and ask questions than a patient who is otherwise normal before they will sign the consent form.

j. If any protocol-specific instruments will be used in the consenting process, such as supplemental handouts, videos, or websites, describe these here and provide a copy of each. If not, enter "None."
None

k. How long will participants have between the time they are told about the protocol and the time they must decide whether to enroll? If not 24 hours or more, describe the proposed time interval and why the 24-hour minimum is neither feasible nor practical. The patient's/parent/legal guardian will have approximately 10 minutes to decide whether to enroll. Due to the constraint of enrolling patients prior to them undergoing the reduction procedure in the ED, we cannot allow for a 24-hour time period to decide whether to enroll. Since enrolling will not affect the care the patient will receive a ten-minute window to decide about enrollment is sufficient.

22. Procedures to Protect Privacy

a. Describe how you will protect the privacy interest of the participants. Include how you will make sure others cannot overhear your conversation with potential participants and that individuals will not be publicly identified or embarrassed. All discussions will remain private between research personnel, the patient, and their guardian(s). Individuals will not be publically identified in any way and thus will not be subject to embarrassment.

23. Procedures to Maintain Confidentiality

a. Describe how you will store research data to maintain confidentiality (both paper records and electronic data), including how access is limited. If data will be stored electronically anywhere other than a server maintained centrally by UAB, identify the department and all computer systems used to store protocol-related data. When enrolled, the patient's information will be entered into a spreadsheet housed solely on Children's of Alabama and/or UAB operated, encrypted, password-protected computers. To maintain confidentiality, the electronic and printed information will only be viewed by the IRB-approved UAB personnel and never left open in an unsecured location. Any printed documents containing identifiers will be destroyed as soon as information has been transferred from print to the patient's secure electronic medical record or to the online spreadsheet. The printed documents will be destroyed using Children's of Alabama and/or UAB-issued paper shredding bins. At the completion of the project, all patient identifiers will be destroyed through the deletion of the data from the Children's of Alabama and/or UAB operated, encrypted, password-protected computers.

b. Will any data from this protocol be given to any person, including the subject, or any group, including coordinating centers and sponsors? Yes No

If Yes, complete i-iii.

i. Who will receive the data? _____

ii. What data will be shared? _____

iii. How will the data be identified, coded, etc.? _____

24. Genomic Data Sharing (GDS)

Researchers who collect genomic data as part of a NIH grant funded after January 25, 2008 may be required to submit those data to a NIH database for broad scientific sharing. See [Genomic Data Sharing](#) in the IRB Guidebook for more information.

a. Does this protocol involve the proposed submission of genetic data into genomic repositories created to share genetic information for research purposes? Yes No

b. Will UAB be uploading the final genomic data to the central repository (e.g., dbGaP)? Yes No

If Yes to both a and b, submit a Detailed Data Sharing Plan to the IRB for review. This plan should include any known data use limitations and indicate whether aggregate-level data are appropriate for general research use. For guidance see the [NIH Genomic Data Sharing Policy](#).

c. Submit a copy of the NIH Institutional Certification Form.

To determine which certification form to include, answer i-ii.

i. Was this protocol funded prior to January 25, 2015? Yes No

- If yes, and consent will be obtained, submit the [Extramural Institutional Certification - Before January 25 - With Consent](#).
- If yes, and consent will not be obtained, submit the [Extramural Institutional Certification - Before January 25 - Without Consent](#).

ii. Was this protocol funded after January 25, 2015? Yes No

- If yes, submit the [Extramural Institutional Certification - After January 25](#).

25. Additional Information

In the space below, provide any additional information that you believe may help the IRB review the proposed research, or enter "None." None

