• The IRB will not accept grant applications and/or sponsor's protocols in lieu of the items as outlined below.

- Do not separate responses from items. Instead, insert your response to each item below the item, keeping the information in the order of this form.

14. Purpose - in nontechnical, lay language

- Summarize the purpose and objectives of this protocol in one short paragraph. The purpose of this study is to determine if Intranasal Ketamine (INK) is efficacious for Procedural Sedation and Analgesia (PSA) when compared to Intravenous Ketamine (IVK) in children with non-operative fractures. The primary aim is to determine if INK provides non-inferior sedation to IVK as defined by a Modified Ramsay Sedation score of ≥ 4 and also to compare the proportion of successful procedure between two treatment groups. The secondary aim is to compare proportion of adverse events and compare duration of sedation and length of ED stay between treatment groups.
- Describe how outcomes will be measured for this protocol. The outcome measured in this study will be successful sedation as defined by Modified Ramsay Sedation score of ≥ 4 . Successful competition of procedure will be defined as completing the procedure with the induction dose and without requiring rescue medication. Any adverse events related to sedation will be documented. Duration of sedation will be the time from administration of induction (first dose) Ketamine to Aldrete score reaching baseline or pre-sedation. ED length of stay will be defined as time to arrival to ED to time of discharge order from ED physician.

15. Background - in nontechnical, lay language

- Summarize in 2-3 paragraphs past experimental and/or clinical findings leading to the design of this protocol. Include any relevant past or current research by the PI. For drug and device studies, summarize the previous results (i.e., Phase I/II or III studies).

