Describe your ability to obtain access to the proposed population that will allow recruitment of the necessary number of participants: **We will have full access to the patients attending the COA ED with fractures requiring reduction. All ED physicians will be informed about the study and eligibility criteria and will have PI and research assistant contact information.**

d. Describe the inclusion/exclusion criteria:

Inclusion Criteria:

- i. **Children 1-18 years of age**
- ii. **Presenting to COA ED and classified as American Society of Anesthesiologists (ASA) I or II non-operative fracture requiring reduction confirmed by X-ray as well as recommended by consulting orthopedic service. ASA I is defined as normal healthy patient and ASA II is defined as a patient with mild systemic disease.**
- iii. **Body weight less than or equal to 25 kg as measured by standard weighing scale**

Exclusion criteria:

- i. **ASA classification III or above**
- ii. **Age less than 1 year**
- iii. **History of hypertension, known coronary artery disease or Kawasaki disease, congestive heart failure, acute glaucoma or globe injury, increased intracranial pressure or intracranial mass lesion, acute porphyria, developmental delays, or major psychiatric disorder**
- iv. **Currently has any condition that causes increased nasal congestion or runny nose (current upper respiratory infection (URI), allergies, etc.).**
- v. **Prior allergy to ketamine**
- vi. **Unavailable parent or guardian to provide consent**
- vii. **Non-English speaking**

e. If participants will comprise more than one group or stratification, describe each group (e.g., treatment/intervention, placebo, controls, sham treatment) **and** provide the number of participants anticipated in each group.

Participants will comprise two groups: 9mg/kg Intranasal Ketamine (100mg/ml) and 1.5mg/kg Intravenous Ketamine (10mg/ml). Participants will be randomized into one of the two groups. For blinding purposes, patients in both groups will have IV access. Participants randomized to Intranasal Ketamine group will receive Intranasal ketamine and IV normal saline whereas participants randomized to IV ketamine will be receive IV ketamine and Intranasal hypertonic (3%) saline. We anticipate to enroll 35 participants in IV ketamine group and 35 participants in Intranasal Ketamine group.

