i. If you will use recruitment materials (e.g., advertisements, flyers, letters) to reach potential participants, attach a copy of each item. If not, identify the source (e.g., IRB Protocol Number for approved databases) from which you will recruit participants. We will post study recruitment flyer (Attached) at different locations in the ED. Flyer will list study eligibility criteria and contact information of the PI as well as research assistant and study coordinator.

j. Describe the screening process/procedures for potential participants. No further screening will take place other than described above.

17. Protocol Procedures, Methods, and Duration - in nontechnical, lay language

a. Describe the procedures for all aspects of your protocol. Tell us what you are doing.

Recruitment and Enrollment

The study investigators will initially screen for participants based on eligibility criteria listed above. Eligible patients will be given information about the study and informed consent and /or assent will be obtained using appropriate forms based on patient's age. Patient will then be randomized by unblinded research pharmacist to receive either 9 mg/kg IN ketamine (100 mg/mL) (maximum 1 mL/naris) or 1.5 mg/kg IV ketamine (10 mg/mL) as an optimal IV induction dose for sedation.

Randomization and Blinding:

Patients will be randomized 1:1 into Intranasal or Intravenous Ketamine using simple randomization. Study group allocation will be concealed by unblinded study pharmacist using sealed envelopes. All Patients, ED staff, including physicians, bedside nurse, study personnel, and any additional staff involved in bedside care will be blinded to the randomization and group assignments. Only research pharmacist will remain unblinded and will not be present during enrollment or patient care. For blinding purposes, and per our center's current practice, all patients will have IV access established. Per hospital protocol, sedation and procedural consents will be obtained, and sedation safety and equipment checklists and procedure "timeout" will be performed prior to initiation of sedation. In our institution, the emergency department physician administering sedation medications and monitoring the patient is uninvolved in the fracture reduction. Research pharmacist will maintain prefilled syringes loaded with the study drug, intravenous normal saline, or intranasal hypertonic (3%) saline. Study drugs will be stored in a

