dedicated automated medication dispensing system in the ED. These syringes will be pre-labelled by a color code without identifying the drug inside. Color code indicates the route of administration (Intranasal or Intravenous). Treatment allocated to the patient will only be known to the research pharmacist. Research pharmacist will maintain a log of randomization ID and patient identifier. Study drugs will be discarded at the conclusion of the sedation per our ED protocol. Sedating physician will document randomization ID in their sedation record. Study pharmacist will use pyxis data entry and documentation to verify drug administration and drug dosage.

Breaking the blinded code:

We do not anticipate any serious adverse events and need for premature code breaking. After all patients are enrolled and data entry is complete, we will break the blinded code just before data analysis.

Sedation induction and monitoring:

Subject randomized to the IN ketamine will receive IN Ketamine. After 8 minutes, IV Normal Saline (NS) will be given over 30 seconds. Subjects randomized to IV Ketamine will first receive IN hypertonic (3%) saline. After 8 minutes, IV Ketamine will be given over 20-30 seconds.

The study personnel will assess the level of sedation at 5-minute intervals, per our ED protocol, after IN medication administration (induction dose) using the modified Ramsay sedation scale until a score of ≥ 4 is achieved, which will serve as our definition of adequate sedation. Modified Ramsay Sedation scale scores range from 1-8 based on wakefulness of the patient. Score of 1 indicates fully awake and alert whereas score of 8 indicates unresponsive to external stimuli including pain. This scoring will be done by trained study personnel. Sedation scoring will be continued at 5-minute intervals until the reduction is completed. Failure of sedation will be defined as not achieving adequate sedation by Ramsay score of < 4 within 10 minutes of IN administration.

Patients who fail sedation at 10 minutes will receive 0.5 mg/kg IV ketamine or more, with additional IV doses as deemed necessary by treating physician. No subsequent IN medications will be given after the induction dose. Duration of successful sedation will be defined as induction dose time to when the patient is appropriate for discharge from sedation as noted by sedating ED physician. Discharge criteria includes patient said to have reached baseline/pre-sedation modified Aldrete Score.

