Procedure: Once sedation is achieved, orthopedic surgeon will start the fracture reduction. Depending on the type of fracture, length of reduction varies from 5-60 minutes. This includes cast placement and molding which can be painful and is to be included as part of the procedure. Successful completion of procedure will be defined as completed reduction and casting as deemed necessary by orthopedist using only the first 2 drug doses that include the induction intranasal drug and IV drug given at the 8-minute mark. For our purposes, a failed sedation will be described as modified Ramsay sedation score of < 4 by 10 minutes from induction dose or where the patient requires a rescue dose of IV Ketamine at any time throughout the procedure as deemed necessary by sedating physician. Rescue doses are often needed and are not generally documented or referred as "failed" sedation. However, we are directly comparing the induction dose of IN Ketamine to induction dose of IV ketamine. The treating ED physician will assess the outcome and either conclude the sedation as failed or successful. After the procedure is completed, the ED physician will assess and deem the patient appropriate for discharge once the patient has been said to have reached baseline/pre-sedation modified Aldrete Score.

Data collection:

We will collect clinical and demographic variables (Attached Data collection sheet).

Clinical variables collected will include patient age, patient weight, imaging obtained, the type of fracture, mechanism of fracture, location of fracture, time of injury, NPO status, prior pain medication administration and time, other associated presenting symptoms, medical history, surgical history, allergies, time to sedation, sedation scores and vital signs at each interval set by ED protocol, whether rescue medication was needed, type of casting placed, adverse events, non-sedation-related delays (c-arm/radiology, casting supplies, nursing, ortho, etc), reduction failure not related to a sedation complication, duration of sedation, sedation discharge score, ED length of stay. Demographic information such as age, gender, race/ethnicity, ED arrival date/time.

Duration of study:

The total duration of the study will be 2 years including enrollment, data collection, and data analysis and writing report.

- b.** What is the probable length of time required for the entire protocol (i.e., recruitment through data analysis to study closure)? 24 months

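### Should 70 children have been allocated by fracture-stratified blocks, with a stratified analysis, instead of by simple randomisation?

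*Combined protocol and SAP*

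**What the plan says.** Allocation is unrestricted: "Patients will be randomized 1:1 into Intranasal or Intravenous Ketamine using simple randomization" (Section 17.a, Randomization and Blinding). An unblinded research pharmacist, absent from enrolment and care, conceals it in sealed envelopes. Section 16.a gives 70 participants, and Section 16.e adds: "We anticipate to enroll 35 participants in IV ketamine group and 35 participants in Intranasal Ketamine group".

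Fracture type is known before allocation, because Section 16.d requires a "non-operative fracture requiring reduction confirmed by X-ray as well as recommended by consulting orthopedic service". It is also recorded; the variables in Section 17.a (Data collection) include "patient weight, imaging obtained, the type of fracture, mechanism of fracture, location of fracture".

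Two outcomes count rescue. Section 14 states: "Successful competition of procedure will be defined as completing the procedure with the induction dose and without requiring rescue medication". Section 17.a (Procedure) counts as failed a Ramsay score below 4 by 10 minutes, and also any case "where the patient requires a rescue dose of IV Ketamine at any time throughout the procedure". A third definition, in Section 17.a (Sedation induction and monitoring), does not mention rescue: "Failure of sedation will be defined as not achieving adequate sedation by Ramsay score of < 4 within 10 minutes of IN administration".

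The documents plan no blocking, stratification or adjustment. They contain no analysis section at all.

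**The concern.** Two things look wrong at first sight. The plan anticipates 35 per arm, yet simple randomisation of 70 children seldom gives exactly that. And the plan itself links fracture type to time under sedation: "Depending on the type of fracture, length of reduction varies from 5-60 minutes". A longer reduction leaves more time for a rescue dose, and one rescue dose makes the case a failure. If fracture type is prognostic, chance imbalance in fracture mix adds noise to the comparison of procedure success, which is part of the primary aim.

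Only precision is at stake. With 95% success in easier fractures, 75% in harder ones and half the children in each group (all assumed), stratified 4/6 blocks plus a Mantel-Haenszel analysis narrow the mean 95% interval from 32.9 to 31.5 points. Fracture type is already collected, so that looks like a gain for little effort.

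**Working it through.** **Inputs from the documents.** N = 70, 1:1, simple randomisation, 35 + 35 anticipated. No success rate, rescue rate by fracture type, margin, alpha or power is given, so the plan has no figure to reproduce beyond the arm sizes. Everything about prognostic strength below is assumed.

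**1. Arm sizes.** With n ~ Binomial(70, 0.5):

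- P(exactly 35/35) = 0.095
- P(30/40 or worse) = 0.282
- P(28/42 or worse) = 0.120

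The variance of a difference in proportions, relative to equal arms, is (70/4)(1/n + 1/(70 − n)). For 42/28 this is 17.5 × (1/42 + 1/28) = 1.042. Averaged over the binomial distribution it is 1.0149. The average cost is therefore 1.5% of variance, or 70 × 0.0149 ≈ 1 child.

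**2. Validity.** In simulation the unadjusted difference after simple randomisation showed no material bias, and its 95% interval covered 93.8-94.9%.

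**3. Which outcomes could gain.** The reduction starts only once sedation is achieved, so its length cannot affect the 10-minute Ramsay result. That is the first-named primary comparison, and by this mechanism it gains nothing. Children who fail at 10 minutes are to receive further IV ketamine, so they also fail procedure success. Part of the rescue-based outcomes is therefore out of reach of fracture type too.

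**4. Size of the possible gain.** Take two fracture groups with success rates a (easier) and b (harder), a share f of children in the harder group, and p = (1 − f)a + fb. The share of outcome variance explained is R² = f(1 − f)(a − b)² / [p(1 − p)]. Simulated variance factors for two strata, relative to a perfectly balanced trial, are 1.0301 for simple randomisation with Mantel-Haenszel and 1.0009 for stratified 4/6 blocks with Mantel-Haenszel. Relative to simple randomisation with an unadjusted comparison:

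- Mantel-Haenszel alone: (1 − R²) × 1.0301 / 1.0149
- Blocks plus Mantel-Haenszel: (1 − R²) × 1.0009 / 1.0149
- Equivalent extra children: 70/ratio − 70

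Example, a = 0.75, b = 0.55, f = 0.5: p = 0.65; R² = 0.25 × 0.04 / 0.2275 = 0.044; Mantel-Haenszel alone 0.956 × 1.0301 / 1.0149 = 0.970; both steps 0.956 × 1.0009 / 1.0149 = 0.943; 70/0.943 − 70 ≈ 4.2 children.

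| Success easier/harder (f = 0.5) | R² | Mantel-Haenszel alone | Blocks + Mantel-Haenszel | Extra children, both steps |
|---|---|---|---|---|
| 75/75 | 0 | 1.015 | 0.986 | 1.0 |
| 75/65 | 0.012 | 1.003 | 0.974 | 1.8 |
| 75/55 | 0.044 | 0.970 | 0.943 | 4.2 |
| 85/75 | 0.016 | 0.999 | 0.971 | 2.1 |
| 85/65 | 0.053 | 0.961 | 0.934 | 5.0 |
| 95/85 | 0.028 | 0.987 | 0.959 | 3.0 |
| 95/75 | 0.078 | 0.935 | 0.909 | 7.0 |
| 95/65 | 0.141 | 0.872 | 0.848 | 12.6 |

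Direct simulation of the 75/55 and 85/65 rows (12,000 trials each) gave 0.97 for Mantel-Haenszel alone and 0.96 for both steps, so the formula is, if anything, generous.

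The larger gains need about 95% success in the easier group. Section 17.a (Procedure) says that rescue doses are often needed, and any rescue counts as failure, so the lower rows of success are at least as plausible. The one figure in Section 15 for intranasal ketamine at 9 mg/kg is 3 of 4 adequately sedated, in laceration repair; it is too small to lean on, but it does not support 95%.

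**5. What blocking itself adds.** 1.0009 / 1.0301 = 0.972, so about 3% of variance whatever R² is. The rest comes from the analysis, and the documents state no analysis for it to replace.

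**6. What blocking costs.** Section 16.h has the investigator or study personnel approach and consent families. Section 17.a has study personnel score sedation every 5 minutes from the intranasal dose, while the IV syringe follows at 8 minutes. Sedation seen before 8 minutes hints at the arm. With 4/6 blocks in two strata, the next allocation is guessed correctly 69% of the time if all earlier arms are known, 57% if they are read with 90% accuracy and 53% with 75% (assumed accuracies). Under simple randomisation it is 50%.

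**The case for a change.** The strongest case for the change is its asymmetry. Done in full, it loses no precision when fracture type is irrelevant (ratio 0.986), and at 95% success in the easier group it is worth about 3 children for a 10-point gap and 7 for a 20-point gap. It needs no new data item. It also gives near-equal arms: 34-36 per arm in 98% of simulated trials. An analysis section has to be written anyway, and the fear of predictability can be met by keeping simple randomisation and only pre-specifying the adjustment.

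The arithmetic stands, and a 20-point gap cannot be excluded. Three things weaken the argument. The protection against loss comes from the blocks, and they are what makes allocation more predictable. Without them, adjustment costs 1.5% if fracture type is not prognostic, is neutral at a 10-point gap and gains 3-4% at 20 points when easier-group success is 75-85%. And the change is not free: the documents define no fracture categories, so a grouping would have to be devised, a second envelope set made, and the stratum relayed to a pharmacist who is not present at enrolment.

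**Conclusion.** The concern does not hold. Simple randomisation with concealed envelopes is a valid choice at N = 70. The 35 + 35 is an expectation and not a design constraint, and departures from it cost about 1.5% of variance on average.

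The extra precision on offer is conditional. It applies only to the rescue-based outcomes. It rests on a link from fracture type to rescue that the documents do not state. At assumed easier-group success of 75-85%, with half the children in each fracture group, both steps together are worth about 2 children at a 10-point gap and 4-5 at 20. Only success near 95% brings 7 or more. With no margin, alpha or power in the documents, nothing shows that an interval narrower by about 1.4 points would change a conclusion.

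Against that gain stands easier guessing of the next allocation, 53-69% instead of 50%, where the staff who recruit also score sedation. Reasonable statisticians would settle this trade-off differently. The authors may choose to pre-specify an adjusted analysis, but leaving the randomisation as it is is no defect.

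### No modified Ramsay score is required before dosing, so a child already at 4 or more can meet the sedation endpoint without any drug effect

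*Combined protocol and SAP*

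**What the plan says.** Item 14 sets the comparison: "The primary aim is to determine if INK provides non-inferior sedation to IVK as defined by a Modified Ramsay Sedation score of" 4 or more. It also compares the proportion of successful procedures, which it defines as needing no rescue medication.

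Under Sedation induction and monitoring, item 17.a states: "The study personnel will assess the level of sedation at 5-minute intervals, per our ED protocol, after IN medication administration (induction dose". Reaching 4 or more "is achieved, which will serve as our definition of adequate sedation". The IV syringe follows 8 minutes after the intranasal one, and a child still below 4 at 10 minutes is a sedation failure. The scale is described as a measure of wakefulness, and only its two ends, 1 and 8, are explained. The table in item 17.e also starts sedation monitoring at the induction dose.

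The criteria in item 16.d say nothing about wakefulness or earlier sedating drugs, and item 16.j adds: "No further screening will take place other than described above". The data collection list in item 17.a includes "prior pain medication administration and time", with no restriction or analysis attached. A pre-sedation reference is mentioned only for the modified Aldrete score, which governs recovery. The data collection sheet is an attachment and is not in the supplied text.

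Under Procedure, item 17.a gives a wider definition: any rescue dose of IV ketamine during the procedure also makes the sedation a failure.

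On size and allocation, item 16.e says "We anticipate to enroll 35 participants in IV ketamine group and 35 participants in Intranasal Ketamine group", and item 17.a says "Patients will be randomized 1:1 into Intranasal or Intravenous Ketamine using simple randomization".

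**The concern.** The endpoint is a level, not a change. A child who is asleep or drowsy enough to score 4 before the first syringe satisfies it at the first post-dose score, whichever syringe held ketamine. Such children carry no information about the route of administration, yet they count as successes. Randomisation spreads them evenly over the arms in expectation, so they pull the two success rates together. In a superiority trial that would be conservative. In a non-inferiority trial it helps the new route pass. Without a pre-dose score, these children cannot be reliably identified afterwards, either to measure the problem or to remove it in a sensitivity analysis.

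**Working it through.** **1. Timing.** Taking the intranasal syringe as time zero, scores fall at 5 and 10 minutes. In the IV arm the intranasal syringe holds saline and ketamine is given at 8 minutes. The 5-minute score therefore precedes any ketamine by 3 minutes. Under the rule in Sedation induction and monitoring, a 4 at that point is already adequate sedation.

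**2. Plan's own figure.** The sample of 70 has no stated margin, alpha, power or assumed rates, so it cannot be reproduced. Nothing below changes it.

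**3. Dilution.** Let π be the true success rate in an arm. Let f be the share at 4 or more before dosing, and g the share of those who succeed regardless of drug. The rest succeed at rate π.

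- Observed rate = f·g + (1 − f·g)·π
- Observed difference = (1 − f·g) × true difference

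Assumptions: IV 95%, which is not in the documents, and intranasal 75%, which is the 3-of-4 laceration-repair result quoted in item 15. Neither f nor g is given.

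| f | g | f·g | IV rate | IN rate | Difference |
|---|---|---|---|---|---|
| any | 0 | 0 | 95% | 75% | 20 points |
| 10% | 1 | 0.10 | 0.10 + 0.90 × 0.95 = 95.5% | 0.10 + 0.90 × 0.75 = 77.5% | 18 points |
| 20% | 0.5 | 0.10 | 95.5% | 77.5% | 18 points |
| 20% | 1 | 0.20 | 0.20 + 0.80 × 0.95 = 96% | 0.20 + 0.80 × 0.75 = 80% | 16 points |

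In the last row the intranasal arm gains 5 points and the IV arm gains 1. The shrinkage comes mainly from the arm with more true failures to convert.

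**4. Consequence for the test (illustration only).** Assume a 20-point margin, one-sided 2.5% and 35 per arm, so that the true difference sits on the margin. The chance of wrongly declaring non-inferiority is Φ((20 points − observed difference)/SE − 1.96), with SE = √[c(1 − c)/35 + t(1 − t)/35], where c and t are the observed IV and intranasal rates.

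- f·g = 0: 2.5%
- f·g = 0.10: SE = 0.0788, 0.02/0.0788 − 1.96 = −1.71, giving 4.4%
- f·g = 0.20: SE = 0.0753, 0.04/0.0753 − 1.96 = −1.43, giving 7.7%

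Exact enumeration of the same Wald rule gives 3.7%, 6.2% and 10.3%.

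**5. Chance imbalance.** Take two independent binomial counts of pre-sedated children with 35 per arm. The probability that the arms differ by 3 or more such children is 31% at f = 10% and 45% at f = 20%. One child is 1/35 = 2.9 points of an arm's rate, and moves it only if that child would otherwise have failed.

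**The case against.** The strongest counterargument is the rescue clause. Under the Procedure definition, a child who was merely asleep must get through reduction and casting, which can last 5 to 60 minutes and can be painful, without rescue ketamine. Many such children would wake, need rescue and count as failures. This stands to the extent that it lowers g: the full (1 − f) shrinkage is an upper bound, and at g = 0 there is no bias. It does not dispose of the point. The sedation definition in item 14 and the wording in Sedation induction and monitoring both omit rescue, so the documents do not settle whether the clause belongs to the primary endpoint.

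Other objections also stand in part:

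- **IV arm.** A child credited at 5 minutes still receives ketamine at 8, so the effect on that arm's rate is small (1 point in the worst case above).
- **IV access.** Establishing it may wake some children, but no text requires that a child be awake at dosing.
- **Data sheet.** The missing sheet may hold a baseline field. A field alone would not set an entry threshold or say how such children are analysed.
- **Chance.** The arms share these children equally only in expectation, so the error in the one trial that is run could go either way.

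A reader might infer that opioid-sedated children will be enrolled, or that item 21.i, where "the treating physician will stabilize patients before informed consent process", means sedating them first. The documents do not support either reading. The data list names no drug class, and item 21.i concerns the consent process and goes on to allow extra time for understanding and questions. Nor do the documents say what behaviour earns a score of 4, so how often a sleeping child would reach it is unknown.

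**Conclusion.** The gap is real. As written, the sedation endpoint can be met without drug effect, and the supplied text has no pre-dose score that would prevent or reveal it. The expected bias is toward non-inferiority. Its size cannot be established from the documents: under the assumed 95% and 75% it runs from 0 to 4 points for f up to 20%, depending on g. A reader might go further and conclude that the non-inferiority comparison is materially biased. That does not follow, because f, g, the IV rate and the margin are all absent from the documents, and the error in a single trial of this size could fall in either direction. This is a cheap improvement worth making, not a flaw shown to invalidate the comparison.

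**What to change.** - **Entry.** Have study personnel record a modified Ramsay score as close as practicable before randomisation, and add a score below 4 to the inclusion criteria. Re-score a sleeping child once awake.
- **Pre-dose record.** Repeat the score immediately before the first syringe.
- **Primary analysis.** Keep every randomised child under the stated endpoint. Do not redefine success as a rise from below 4: a child below 4 at randomisation but at 4 or more on the repeat could not then be classified.
- **Sensitivity analysis.** Prespecify one that excludes children at 4 or more on the repeat score. That score precedes any study drug, so the exclusion does not depend on treatment. Add a descriptive summary by prior analgesic, which is already collected.
- **Definitions.** Reconcile the definitions of sedation success and failure in item 14 and in the two parts of item 17.a, stating whether rescue belongs to the primary sedation endpoint.

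The cost is one brief assessment, taken twice, on a scale staff already use, one line in the criteria, and a few sleepy children delayed or not randomised.
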